1.4 Preliminary Data

N/A

HRP-503a - TEMPLATE - Interventional Research Protocol 1.1.21 Protocol Title: Povidone-lodine for nasal decolonization

1.5 Sample Size Justification

We assumed that *S.* aureus/MRSA suppression in 20% of patients would be clinically relevant and that up to 5% of patients may have suppression even without treatment. Using a one-sided alpha of 0.05 and a beta of 80%, we calculated that we would need at least 85 patients in each group for a total of at least 170 patients. A paired t-test will be used to compare preintervention nasal culture CFUs to 1- hour post application, 2- hour post application, and 3-hour post application, nasal culture CFUs. A 2-sample t test will be used to compare the difference in pre- and post- intervention CFUs between the control and experimental groups at any endpoint. Additionally, mixed regression analysis will be used to determine the effect of the intervention on the CFU counts over all follow-up time points.

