1.2 Research Significance

According to some estimates, as many as 25%-30% of healthy individuals in the community have nares colonized with *S. aureus*, while 1%-2.6% have MRSA-colonized nares[1]. This nasal carriage of *S. aureus* and MRSA is a known risk factor for post-operative wound infections in several different types of surgery[2]. Many, if not most infections due to *S. aureus* occur in colonized persons[1]. In implant-based breast reconstruction surgeries for instance, nasal carriers of *S. aureus* are 3 to 6 times more likely than noncarriers to develop nosocomial infections with this pathogen[3]. Similarly, studies have revealed that MRSA nasal colonization may be an independent risk factor for surgical site infection[4]. In a particular study, the MRSA PCR-positive group had a 9-fold increased risk of MRSA surgical site infection compared to the MRSA PCR-negative group, though the former had a low incidence at 1.86%[4]. Coagulase-negative staphylococci (CoNS) are also important etiological agents of post-operative infection[5, 6]. Together, *S. aureus* and CoNS (predominantly *S. epidermidis*, a common denizen of human skin that can colonize nares as well) account for 50-60% of prosthetic joint infections in roughly equal proportions[5, 6].

The agent typically used in assessing the effectiveness of nasal decolonization is mupirocin, which has been shown in some studies to eradicate colonization in up to 92% of post-operative nasal cultures[7]. Randomized controlled trials comparing nasal mupirocin with placebo in general, gynecologic, neurologic, orthopedic, and cardiothoracic procedures have demonstrated that mupirocin reduces the rate of surgical-site infection among known carriers of *S. aureus*[2]. In fact, the American Society of Health-System Pharmacists recommends screening and nasal mupirocin decolonization for *S. aureus*-colonized patients before total joint replacement and cardiac procedures[8]. Likewise, some studies indicate that nasal mupirocin can decolonize CoNS, with only 1.3% of CoNS isolated from the nares of orthopedic surgery patients and 1.6% of samples from prosthetic joint infections displaying some resistance to mupirocin[5].

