1.3 Research Design and Methods

Implement povidone-iodine (10%) pre-operative nasal decolonization for patients undergoing same-day surgery and evaluate efficacy and tolerability of this intervention in eradicating nasal colonization.

HRP-503a - TEMPLATE - Interventional Research Protocol 1.1.21 Protocol Title: Povidone-lodine for nasal decolonization

A. Research Procedures

This will be a prospective single-blinded randomized placebo-controlled trial of two applications of a nasal 10% PI solution used on the intranasal mucosal surfaces of each nostril in the preoperative holding area within 2 hours prior to surgical incision compared with sterile saline using the same technique. Both the PI and sterile saline will be applied by rotating the swab over the intranasal mucosal surface for 15 seconds; this process will be performed twice for both nostrils, using a new swab for each of the 4 applications. 200 subjects will be chosen from a pool of patients arriving at University Hospital, Newark, NJ for outpatient surgery. Inclusion criteria include community-based patients ages 18-80, ASA 1-3 who will be undergoing an outpatient surgery scheduled for at least 1 hour and up to 6 hours duration. Exclusion criteria include pregnancy, allergy to povidone-iodine, infectious indication for surgery or preexisting known infection/wound, known immunocompromised state, use of antibiotics, chemotherapy, or steroids within 1 month prior to surgery. Additionally, patients presenting for surgeries where field avoidance prevents intraoperative access to the nares (e.g., ENT/OMFS/ophthalmology procedures) will be excluded. Patients will be randomly divided into two groups: control (sterile saline) vs. experimental (PI) This will be done via simple randomization using a computer program that assigns patients as they present into either the control or experimental group while maintaining an overall approximately even ratio of subjects in each group.

B. Data Points

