The primary study end point is the decrease in S. aureus/MRSA colony forming units (CFU) in nasal swab specimen taken perioperatively after intervention in patients who presented with a positive pre-interventional nasal swab specimen. A secondary endpoint is the presence or absence of surgical site infections at 7 and up to 30-day postop intervals (per retrospective chart review). The review includes an assessment of post-operative infections, complications, and prescribing antibiotics (name, dose, number of days, completing).

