4.0 Subject Considerations

4.1 Subject Selection and Enrollment Considerations

A. Method to Identify Potential Subjects

Subjects will be chosen from a pool of patients arriving at University Hospital, Newark, NJ for outpatient surgery.

B. Recruitment Details

Subjects meeting the inclusion criteria will be identified by the anesthesiologist preoperatively and be given information about the study and what their participation entails. They will also be given a recruitment flyer with information and will have the opportunity to ask any questions they may have.

C. Subject Screening

- Inclusion Criteria
- community-based English or Spanish speaking patients ages 18-80
- · willing and able to consent
- American Society of Anesthesiology (ASA) 1-3
- undergoing an outpatient surgery for at least 1 hour and up to 6 hours duration

Exclusion Criteria:

- pregnancy
- allergy to povidone-iodine
- infectious indication for surgery or preexisting known infection/wound
- immunocompromised state
- use of chemotherapy or steroids within 30 days prior to surgery
- use of antimicrobial therapy within 30 days prior to surgery
- surgeries where field avoidance prevents intraoperative access to the nares

D. Privacy Protections

No information about the patients will be revealed to anyone except the study team and providers involved in the care of the patients.

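### The stated inputs (20% vs 5%, one-sided 0.05, 80% power) give 60 to 72 per group, not 85; at 85 the power is about 91%, and the figure labelled beta is the power

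*Combined protocol and SAP*

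**What the plan says.** Section 1.5 assumes that "suppression in 20% of patients would be clinically relevant and that up to 5% of patients may have suppression even without treatment". It then states: "Using a one-sided alpha of 0.05 and a beta of 80%, we calculated that we would need at least 85 patients in each group", 170 in total. Section 6.1 repeats both the rates and the number. Section 4.3 A repeats the alpha, the beta and the number without the rates. No test, formula, software or allowance for loss is given for the calculation. Allocation is approximately even (section 1.3 A).

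Four other statements bear on what the number means:

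- Section 1.3 A plans that "200 subjects will be chosen from a pool of patients", and does not link 200 to the calculated 170.
- Section 1.3 D defines the primary endpoint as the decrease in CFU "in patients who presented with a positive pre-interventional nasal swab specimen".
- The eligibility criteria in sections 1.3 A and 4.1 C do not require carriage.
- Sections 1.5 and 6.1 analyse CFU by paired and two-sample t-tests and mixed regression. They name no test of suppression proportions.

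**The concern.** This is the plan's only sample size justification. Alpha, sidedness, both rates and (once the wording is corrected) power are all given, so the number should follow from them, and it does not. A reader cannot tell whether the power was misstated or an allowance was applied and not reported.

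The label is also wrong. Beta is the type II error rate, so a beta of 80% means 20% power.

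The correction itself carries a risk. A bare restatement of the power as 91% would suggest more assurance than the plan supports, because that figure belongs to a binary comparison in all randomised patients and not to the primary endpoint.

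**Working it through.** **Inputs.** p1 = 0.20, p2 = 0.05 and one-sided alpha 0.05 (section 1.5); equal groups (section 1.3 A). Then p̄ = 0.125, z for alpha = 1.6449, and z for 80% power = 0.8416.

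**Attempt to reproduce 85.**

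1. Pooled normal approximation: n = [z_α√(2p̄(1−p̄)) + z_β√(p1(1−p1) + p2(1−p2))]² / (p1−p2)².
   - z_α term: 1.6449 × √0.21875 = 0.7693.
   - z_β term: 0.8416 × √0.2075 = 0.3834.
   - n = (0.7693 + 0.3834)² / 0.0225 = 59.05, so **60 per group**.
2. Continuity-corrected: n′ = (n/4)[1 + √(1 + 4/(n(p1−p2)))]² = (59.05/4)(1 + √1.4516)² = 71.77, so **72 per group**.
3. One-sided Fisher exact, by enumeration: power is 0.7996 at 66 and 0.8060 at 67, so **67 per group**.
4. Beta taken literally as 0.80: (0.7693 − 0.3834)² / 0.0225 = 6.62, so 7 per group. The literal reading can be set aside.

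None of these gives 85. The unpooled (58) and arcsine (55) formulas are further away.

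**Power at 85 per group.** z = (0.15√85 − 0.7693)/0.4555 = 1.347, so power = **0.911**. One-sided Fisher exact gives **0.887**.

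**Changing one input.** One-sided 0.05 with 90% power gives 82 (95 continuity-corrected). Two-sided 0.05 with 80% power gives 76 (88 continuity-corrected). An unstated allowance for loss could produce a figure at or near 85: 72/(1 − 0.15) = 84.7, so 85; or 67/(1 − 0.20) = 83.75, so 84. The documents mention neither.

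**What the denominator does.** Section 1.2 says that "as many as 25%-30% of healthy individuals in the community have nares colonized with" *S. aureus*. Two assumptions are needed to go further: that 25–30% applies to this surgical population, and what the 20% and 5% are rates of. Expected carriers per group:

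- 170 enrolled: 85 × 0.25 = 21.25 to 85 × 0.30 = 25.5.
- 200 enrolled: 100 × 0.25 = 25 to 100 × 0.30 = 30.

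| Meaning of 20% and 5% | Rates among carriers | One-sided power, 21–30 carriers per group |
|---|---|---|
| Rates among carriers | 20% vs 5% | 0.43–0.55 normal approximation; 0.24–0.36 Fisher |
| Rates among all enrolled, only carriers can be suppressed, 25% carriage | 0.20/0.25 = 80% vs 0.05/0.25 = 20% | Fisher 0.987 at 21, 0.997 at 25 |
| Same, 30% carriage | 0.20/0.30 = 67% vs 0.05/0.30 = 17% | Fisher 0.980 at 26, 0.987 at 30 |

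If 25.5 is rounded down to 25, the 0.980 becomes 0.974.

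**The case against.** The strongest reply is that nothing is lost. The text says at least 85, and 85 exceeds every requirement derived from the stated inputs. No statistician would be misled by the beta slip. This stands as far as it goes: the error is conservative, and on the arithmetic alone it is a reporting correction. It does not remove the error, because the plan presents 85 as the calculated minimum, and on these inputs it is not.

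A second reply is that the 200 subjects in section 1.3 A cover losses. The documents do not say so. If they did, 85 would be the figure before inflation, and the inputs still would not give it.

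A third is that the calculation was really two-sided. That contradicts the one-sided alpha stated in three sections, and by itself gives 76 or 88, not 85.

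Three stronger readings are tempting, and the documents do not support them:

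- *The trial is oversized and could be cut to 60 per group.* The 60 counts every patient as evaluable for a binary outcome, while the primary endpoint uses only swab-positive patients.
- *The trial has only about 43–55% power.* That needs the 20% and 5% to be rates among carriers. Section 1.5 speaks of patients and fixes no denominator; the other reading gives about 98% or more.
- *The primary analysis has 91% power.* No test of suppression proportions is planned, so that figure does not describe the CFU analyses.

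**Conclusion.** The point holds as a correction of the stated pair of sample size and power, not as a claimed shortfall. On 20% against 5%, one-sided 0.05 and 80% power, the requirement is 60 to 72 per group depending on the test, which is 13 to 25 below the stated 85. At 85 per group the power is about 91% (89% by Fisher), not 80%. The term beta is wrong in all three sections.

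These figures assume equal groups and a binary suppression outcome with all 85 per group evaluable. They do not carry over to the primary endpoint. The carrier-only figures depend on the assumed carriage and on an unstated denominator, and range from about 24% (Fisher, rates among carriers) to over 99% (Fisher, rates among all enrolled). They show why the denominator must be stated, and do not establish a power for this trial.

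**What to change.** In sections 1.5, 4.3 and 6.1:

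1. Replace the beta wording with *power 80% (beta 20%)*, and name the test behind the calculation.
2. If an allowance was actually used to reach 85, state it. If not, keep 85 and restate the power as about 91% (89% by Fisher exact) at one-sided 0.05. An input should not be chosen afterwards to fit 85, and a two-sided alpha should not be offered as the explanation.
3. Beside any restated power, say that it applies to a binary suppression comparison with all 85 per group evaluable, whereas the primary endpoint is CFU decrease in swab-positive patients, analysed by t-tests and mixed regression.
4. Say whether 20% and 5% are rates among carriers or among all enrolled patients, and give the expected number of swab-positive patients per group.
5. If a carrier-only power is shown, label both assumptions (carriage and denominator) and give the whole range.

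The cost is a text change in three sections. Enrolment is unchanged.

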1.6 Study Variables

A. Independent Variables, Interventions, or Predictor Variables

Independent variable will be whether the patient received a nasal swab with Povidone-Iodine or sterile saline.

B. Dependent Variables or Outcome Measures

The decrease in CFUs in multiple time spans after intervention.

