1.8 Specimen Collection

A. Primary Specimen Collection

- **Types of Specimens**: 4 sets of nasal mucosal samples per subject to be collected by a investigator at preoperative, intraoperative, and postoperative intervals.

 A study participant number will be associated with each sample.
- Transport: All cultures will be sent to an outside lab for testing per the following protocol. All swabs will be placed in a 15 mL conical screw-top tubes containing sterile Phosphate Buffered Saline (PBS) solution. The samples will then be shipped the same day by 3 PM in a foam-insulated cooler with ice packs via overnight delivery to the testing facility.
- Processing: Swabs will be analyzed and enumerated by an outside testing facility for the presence of *S. aureus*, MRSA, and *S. epidermidis*.
- **Storage**: The specimens will be stored in the cooler described above and will be shipped out to the lab that same day. Prior to shipping, they will only be accessed by the study team.
- Disposition: Samples will be discarded after the lab has analyzed them.

B. Secondary Specimen Collection

■ N/A

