6.0 Data Management Plan

6.1 Data Analysis

We expect a statistically significant decrease in S. aureus/MRSA colonization in cultures taken perioperatively after intervention in patients who received pretreatment with PI as compared to patients who received sterile saline. We assumed that S. aureus/MRSA suppression in 20% of patients would be clinically relevant and that up to 5% of patients may have suppression even without treatment. Using a one-sided alpha of 0.05 and a beta of 80%, we calculated that we would need at least 85 patients in each group for a total of at least 170 patients. A paired t-test will be used to compare preintervention

HRP-503a - TEMPLATE - Interventional Research Protocol 1.1.21

Protocol Title: Povidone-Iodine for nasal decolonization

Protocol Version Date: v5 05.10.23

9/5/2024

nasal culture CFUs to 1- hour postintervention, 2- hour postintervention, and 3-hour postintervention nasal culture CFUs. A 2-sample t test will be used to compare the difference in pre- and post-intervention CFUs between the control and experimental groups at any endpoint. Additionally, mixed regression analysis will be used to determine the effect of the intervention on the CFU counts over all follow-up time points.

The data will be stratified by type of surgery, duration of surgery, and number of surgeons present throughout the procedure. Additionally, the variables age, sex, race, comorbidities, postoperative hospital stay length, and intraoperative time will be used in data analysis. In addition, postoperative surgical site infection (SSI) surveillance for the study participants will be conducted at 7 and 30-day postop intervals.

An intent to treat analysis will include those who are enrolled in the study and meet eligibility requirements for the study. A per protocol analysis will include all eligible patients who complete the assigned study regimen. Completion of the study regimen is defined as 2 applications of sterile saline or PI preoperatively and at least two cultures obtained perioperatively.

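### No scale is named for CFU and no rule for zero or below-detection counts; read literally, the between-arm t-test runs on raw counts and can lose much of its power

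*Combined protocol and SAP*

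**What the plan says.** Section 1.3 D defines the outcome: "The primary study end point is the decrease in S. aureus/MRSA colony forming units (CFU) in nasal swab specimen", restricted to the group "in patients who presented with a positive pre-interventional nasal swab specimen". Section 1.6 B gives the dependent variable as "The decrease in CFUs in multiple time spans after intervention".

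Section 1.5 sets the between-arm comparison: "A 2-sample t test will be used to compare the difference in pre- and post- intervention CFUs between the control and experimental groups". It also plans within-arm paired t-tests at 1, 2 and 3 hours. Section 6.1 repeats these tests and adds, as 1.5 does, that "mixed regression analysis will be used to determine the effect of the intervention on the CFU counts over all follow-up time points".

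On the laboratory side, section 1.8 A says only "Swabs will be analyzed and enumerated by an outside testing facility", with no detection limit. Section 1.4 (Preliminary Data) is marked not applicable. Nowhere is there a log or other transformation, a rank or count model, a rule for zero counts, or a mean, SD or range for CFU. None of the listed analyses is named as primary.

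**The concern.** Bacterial counts can differ between carriers by orders of magnitude, and a working antiseptic may push many follow-up counts below detection. If PI kills a fraction of the organisms present, each patient's fall in raw CFU is proportional to the starting load. The arm mean of raw differences then depends heavily on which arm drew the few heaviest carriers, and a t-test on it has a large error variance.

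The stake is a null result that cannot be read as lack of efficacy. A second stake is flexibility: with scale and zero rule unstated, both could be chosen after the counts are known.

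**Working it through.** **1. The plan's own figure.** Inputs from section 1.5: suppression 20% versus 5%, one-sided alpha 0.05, and 80% (labelled beta, read as power).

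n = [z(0.95)·√(2·p̄·q̄) + z(0.80)·√(p1·q1 + p2·q2)]² / (p2 − p1)², with p̄ = 0.125

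= [1.645 × 0.4677 + 0.842 × 0.4555]² / 0.15² ≈ 59.1, so 60 per group (72 with continuity correction).

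The stated 85 is not reproduced; at 85 per group these inputs give 91% power. That is a separate matter. What counts here is that the sample size rests on a proportion, so it says nothing about the spread of CFU.

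**2. Carriers available.** Section 1.2 cites 25%-30% carriage; 170 (1.5, 4.3) to 200 (1.3 A) are enrolled at about 1:1. 170 × 0.25 / 2 = 21.25 and 200 × 0.30 / 2 = 30, so about 21-30 per arm.

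**3. What each scale rewards.** A fall from 100,000 to 50,000 CFU is 50,000 on the raw scale. Clearance from 100 CFU is 100, a ratio of 500 to 1. On log10, the first is 0.30. If the detection limit is 10 CFU (assumed) and half of it is substituted, the second is log10(100) − log10(5) = 1.30.

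**4. Dominance by a few carriers.** With simulated lognormal baselines, the three most extreme of 42-60 carriers supplied this median share of the total sum of squares of raw change:

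| Between-patient SD (log10) | Share |
|---|---|
| 0.3 | 52%-75% |
| 0.5 | 67%-81% |
| 1.0 | 91%-94% |
| 1.5 | 96%-97% |

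**5. Power for a uniform PI effect.** Assumptions, none from the documents: mean baseline 3.5 log10, detection limit 10 CFU, PI fall 1.0-1.3 log10, 21-30 carriers per arm, one-sided 0.05.

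| Saline fall (log10) | Swab SD | Between-patient SD | Raw t-test power |
|---|---|---|---|
| 0.3 | 0.5-0.7 | 0.5-1.5 | about 4%-26% |
| 0 | 0.3 | 1.0 | 31%-38% |
| 0 | 0.5 | 0.5 | 36%-50% |
| 0 | 0.3 | 0.5 | about 63%-80% |

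A t-test on log10 change had about 69%-100% across these settings. With no effect, the raw test rejected about 1%-5% of the time, which is conservative.

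A second simulation used kinder assumptions (median baseline 10³ CFU, no change on saline, within-patient noise SD 0.3-0.5, PI falls of 0.5-2 log10). Raw power was 54%-98% at between-patient SD 0.5, 23%-57% at SD 1.0 and 11%-28% at SD 1.5; log10 power was 91%-100%. For falls of 1-2 log10, the raw test missed the effect in 2%-17%, 43%-59% and 72%-82% of runs at those three SDs, and the log10 test in under 1%.

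**6. Power for the protocol's own effect.** Section 1.5 says "suppression in 20% of patients would be clinically relevant", against up to 5% untreated. Simulated as full suppression in those shares and noise only in the rest, between-patient SD 0.5-1.5:

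| Carriers per arm | Raw | log10 |
|---|---|---|
| 21-30 | 3%-12% | 33%-51% |
| 85 | 4%-21% | 79%-90% |

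A direct comparison of the two proportions with 21-30 per arm has 43%-55% power, so the number of carriers is the limit there, whatever the scale.

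**7. Mixed regression.** No mixed model was fitted. As a proxy for a normal-error version, the mean of three follow-ups adjusted for baseline (swab SD 0.6) gave raw power of 73%-93% at between-patient SD 0.5, 34%-61% at SD 1.0 and 19%-32% at SD 1.5, against 95%-100% on log10. This applies only if the model is fitted with normal errors to raw counts.

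**The case against.** The strongest reply is that the plan is silent rather than wrong. It names a measurement and no scale, and an analyst may well have meant log10. Nor does a mixed regression on counts imply normal errors; a log-link count model fits those words. This stands. The defect is an unstated scale, with raw differences as the literal reading of the t-test sentence.

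A reader might infer that a real PI effect will probably be missed. The documents do not support that, because they give neither the spread of CFU nor an expected log reduction. For a fall of 1-2 log10 in the second simulation, a miss was likely at SD 1.5, near even at SD 1.0 and unlikely at SD 0.5. The lowest raw powers also depend on assuming a saline fall of 0.3 log10 and swab noise of at least 0.5.

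A reader might also infer an inflated false-positive rate. The simulations show the reverse. Nor can one say that heavy carriers decide the primary result, since no analysis is designated primary.

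Finally, substituting half the detection limit is somewhat arbitrary when many counts are zero, and a count or censored model is also defensible. That is a fair reservation about the remedy, but it does not favour raw counts: log10 had more power in every setting tried.

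**Conclusion.** The point holds as a gap with a clear better choice. Sections 1.5 and 6.1 leave the CFU scale and the treatment of zero or below-detection counts unstated, and the literal between-arm test uses raw differences. The direction is firm: with 21-30 carriers per arm and a 1.0-1.3 log10 fall, log10 power is about 69%-100% and raw power about 4%-80%. The size is not firm, because it depends on between-patient SD, swab noise and saline effect, all assumed. The harm to expect is a false null.

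One should not infer that moving to log10 makes the trial adequately powered for its stated target. At 20% versus 5% suppression, about 33%-51% power remains, because only baseline-positive patients count. That sample-size problem needs its own answer.

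**What to change.** In sections 1.5 and 6.1:

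- State that the between-arm comparison and the mixed regression are run on log10 CFU, preferably adjusted for baseline log10 CFU.
- Obtain the laboratory's detection limit and fix a rule for counts below it (for example, half the limit) before unblinding.
- Report the arm difference as a log10 reduction or a ratio of geometric means.
- Tabulate the share of swabs below detection by arm and time. This shows how far the result leans on the substituted value. A censored (Tobit-type) mixed model is an optional sensitivity analysis.

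The cost is a few sentences and one figure from the laboratory, with no added patients or swabs. The downsides are small: the effect is read as a ratio rather than a count difference, and the substituted value carries some arbitrariness if zeros are common.

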1.0 Research Design

1.1 Purpose/Specific Aims

To evaluate the efficacy and tolerability of 10% povidone-iodine in eliminating nasal carriage of *S. aureus* and MRSA.

A. Objectives

To determine whether a more convenient, single-dose, pre-operative 10% povidone-iodine (PI) application is effective in reducing nasal carriage of *S. aureus* and MRSA.

B. Hypotheses / Research Question(s)

We expect a statistically significant decrease in *S.* aureus/MRSA colonization in nasal cultures taken perioperatively after intervention in patients who received pretreatment with PI as compared to patients who received sterile saline.

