Potential subjects will be identified from surgical schedule. Patients will be asked for informed consent in the same-day surgery (SDS) unit. They will be given sufficient time to read the IC document and ask questions. While in the preoperative holding area, patients will be asked to sit upright at a 45-90° angle to prevent drainage into the nasopharynx. All patients will first be swabbed for a nasal swab specimen, once in each nostril. Patients will then receive the appropriate nasal applications depending on the group into which they were sorted: Povidone-Iodine or saline. The tolerability assessment of investigating drug will be done with every subject at the Pre-operating room and PACU by a few criteria as burning/itching, pain, irritation, epistaxis, runny nose, and others. Nasal swab specimen will be obtained by the anesthesiologist intraoperatively 1, 2 and 3 hours after investigational drug application as studies have shown that there a significant decrease in colony-forming units of MRSA even within 1-hour post-treatment [9, 10]. These cultures may be intraoperative or postoperative depending on the length of surgery. There will also be a nasal swab specimen obtained while the patient is in the PACU. Study subjects will be stratified according to age, sex, comorbidities, and ethnicity. Additionally, the type of surgery, duration of surgery (Incision start to incision close), number of surgeons present during the procedure (Include all individuals scrubbed in), postoperative hospital stay length, and intraoperative time (patient in OR to patient out OR) will be used in data analysis. The purpose is to identify variables that increase the incidence of surgical site infection.

C. Study Duration

The study will take approximately 2 years, but chart review may continue up to 4 months after the last patient in the study has their procedure. Chart review of subject's postoperative surgical clinic visits will be performed up to 30 days to monitor for any surgical site infection.

D. Endpoints

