1.9 Data Collection

HRP-503a - TEMPLATE - Interventional Research Protocol 1.1.21 Protocol Title: Povidone-lodine for nasal decolonization

A. Primary Data Collection

[figure not shown]
- **Location**: Data collection will occur in the preoperative holding area, operating rooms, and post-anesthesia care unit of the University Hospital, Newark, NJ.
- **Process of Data Collection**: The investigator who is applying the saline or 10% PI to the study subjects will not be blinded. Nasal cultures will be obtained by the study team members. [name] will be overseeing the entire study.
- Timing and Frequency: There will be swab collections prior to the procedure, at the one-, two-, and three-hour marks after saline or 10% PI is administered.
- Procedures for Audio/Visual Recording: N/A
- Study Instruments: n/a
- Ethnographic Studies, Interviews, Or Observation: N/A
- Subject Identifiers: MRN only

B. Secondary Data Collection

N/A

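### The primary CFU endpoint has no named time point and no deciding test, and the sections disagree on whether a PACU swab exists to be analysed

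*Combined protocol and SAP*

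**What the plan says.** Section 1.1 B states one efficacy hypothesis: a decrease in "colonization in nasal cultures taken perioperatively after intervention in patients who received pretreatment with PI" compared with saline. Section 1.3 D makes the primary endpoint the decrease in "colony forming units (CFU) in nasal swab specimen taken perioperatively after intervention", among patients whose pre-intervention swab was positive. Neither gives a time. Section 1.6 B makes the outcome plural: "The decrease in CFUs in multiple time spans after intervention".

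Sections 1.5 and 6.1 list the same three analyses:

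- paired t-tests of baseline against 1, 2 and 3 hours;
- a 2-sample t-test "to compare the difference in pre- and post- intervention CFUs between the control and experimental groups at any endpoint";
- additionally, a mixed regression over all follow-up times.

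No section ranks them, orders them or adjusts for their number. A one-sided alpha of 0.05 appears only in the sample-size statement, which concerns the proportion of patients with suppression.

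The swab schedule differs between sections. After listing swabs at 1, 2 and 3 hours, 1.3 B adds: "There will also be a nasal swab specimen obtained while the patient is in the PACU". Section 1.8 A has "4 sets of nasal mucosal samples per subject to be collected". Section 1.9 A lists a swab before the procedure and swabs "at the one-, two-, and three-hour marks after saline or 10% PI is administered", with no PACU swab.

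**The concern.** One hypothesis and one primary endpoint are to be judged by several tests, and the plan does not say which one decides. Suppose the arms differ significantly at 1 hour but not at 2 or 3 hours, or the mixed model and the t-tests point different ways. Nothing written in advance then says whether the trial met its primary endpoint. The rule would have to be supplied after the data are seen, and picking the most favourable result raises the chance of a false claim.

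The PACU swab adds to this. If it is collected, the wording of both the 2-sample t-test and the mixed model could include or exclude it, and it is not taken at a fixed time after application.

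**Working it through.** **The plan's own figures.** The plan gives no figure for disagreement between its tests or for their joint error rate. Its only sizing (5% against 20% suppression, one-sided 0.05, 80% power, 85 per group) is for a binary outcome that none of the three listed analyses tests. It therefore gives no power for the CFU tests.

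**Swab count.** Section 1.3 B: baseline + 3 timed + PACU = 5 collections. Section 1.8 A: 4 sets. Section 1.9 A: baseline + 3 = 4. The paired t-tests use only the 1, 2 and 3 hour swabs.

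**PACU timing.** Application is "within 2 hours prior to surgical incision" (1.3 A), and surgery is planned for 1 to 6 hours (1.3 A, 4.1 C). Surgery therefore ends between 0 + 1 = 1 hour and 2 + 6 = 8 hours after application. A PACU swab can fall before or after the 3-hour swab.

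**Disagreement among the three between-arm t-tests.** These inputs are assumed, because the documents give no CFU standard deviation, effect size or correlation: approximately normal test statistics, the same true effect at 1, 2 and 3 hours, one common correlation ρ between statistics, and the same power π per test. Put t = −Φ⁻¹(π). Then

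- P(none significant) = ∫ φ(u) Φ((t − √ρ·u)/√(1−ρ))³ du
- P(all significant) = ∫ φ(u) [1 − Φ((t − √ρ·u)/√(1−ρ))]³ du
- P(disagree) = 1 − P(none) − P(all)

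| Power per test | ρ | P(none) | P(all) | P(disagree) |
|---|---|---|---|---|
| 50% | 0.5 | 0.2500 | 0.2500 | 0.5000 |
| 50% | 0.9 | 0.3923 | 0.3923 | 0.2153 |
| 80% | 0.5 | 0.0501 | 0.6114 | 0.3385 |
| 80% | 0.9 | 0.1283 | 0.7215 | 0.1502 |
| 95% | 0.5 | 0.0050 | 0.8816 | 0.1134 |
| 95% | 0.9 | 0.0251 | 0.9205 | 0.0544 |
| 99% | 0.5 | 0.0004 | 0.9735 | 0.0261 |
| 99% | 0.9 | 0.0040 | 0.9823 | 0.0137 |

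This needs no success rule. Alpha and sidedness enter only through the assumed power. The mixed model is left out because its terms are not specified.

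**Which power applies?** The documents do not settle it. If the 25% to 30% community carriage quoted in 1.2 applied, 170 patients would give 170 × 0.25 = 42.5 to 170 × 0.30 = 51 baseline-positive patients, about 21 to 26 per arm, so low power is possible. Section 1.3 B, on the other hand, cites a significant fall in MRSA counts within 1 hour, so high power is also possible.

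**Illustration of a one-win rule, which the plan does not state.** If any one of three one-sided 5% tests counted as success, the false-positive rate would be 1 − ∫ φ(u) Φ((1.645 − √ρ·u)/√(1−ρ))³ du. That is 0.118 at ρ = 0.5, 0.103 at 0.7 and 0.080 at 0.9.

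**The case against.** The strongest reply is that the plan already contains one overall analysis, the mixed model across all follow-up times, and that differences between time points are ordinary in repeated-measures data. This is partly right: disagreement is no defect in a trial that has said which result decides. Here, however, the mixed model is introduced as an addition, is not called primary, and its target (an average effect or a treatment-by-time interaction) is not stated.

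A second reply is that the size of the problem rests on assumed power. That stands. At 99% power per test the three t-tests would almost always agree, so the documents do not support a statement that conflict is common.

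A reader might infer that the wording of the 2-sample test makes one significant time point enough, so that the error rate is inflated as planned. The text does not say so. The phrase can equally mean a test at each time point, and the sidedness of these tests is not given.

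A reader might also count PACU as a fourth tested time. No section says that. Sections 1.8 and 1.9 and the paired t-tests agree on baseline plus three timed swabs, and only 1.3 B adds PACU. The timeline figure in 1.10 was not available and may show the intended schedule. The conflict in the text remains.

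**Conclusion.** The concern holds as a gap in prespecification. One primary endpoint has no time point and three unranked analyses, without multiplicity control and without a stated alpha or sidedness, and nothing elsewhere in the documents supplies the missing rule.

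Its practical size is uncertain. Disagreement among the three between-arm t-tests ranges from about 1% to 50% of trials over the power (50% to 99%) and correlation (0.5 to 0.9) assumed here. The false-positive rate of about 8% to 12% applies only under a one-win rule that the plan does not contain, so it should not be cited as the plan's error rate.

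This should be fixed before analysis. The case rests on the missing rule and does not depend on any one of these percentages.

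**What to change.** In 1.3 D, 1.5 and 6.1, name one between-arm primary test and give its alpha and sidedness. One option uses what is already planned: the mixed model's average treatment effect over the 1, 2 and 3 hour swabs in baseline-positive patients, adjusted for baseline CFU and tested once. One named time point, or a fixed testing order, would also do.

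Make the per-time between-arm t-tests secondary (Holm-adjusted or descriptive), make the within-arm paired t-tests descriptive, and delete the words 'at any endpoint'.

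Reconcile the number of swabs across 1.3 B, 1.8 and 1.9, and check it against the timeline figure in 1.10. State whether the PACU swab enters the primary analysis and, if it does, how its variable time is handled.

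The cost is a few sentences in these sections, and naming the test requires no extra swabs. The downside is that an effect at a single time is diluted in the average and can no longer be claimed as the primary result. The power of the chosen test is a separate question that the present sizing, made for a suppression proportion, does not answer.
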